### 1.4.2 Background on Nivolumab

For a complete review of non-clinical and clinical information, please refer to the BMS-936558 Investigator Brochure (IB).

**a) Non-clinical:** Preclinical animal models of tumors have shown that blockade of Programmed death-1 (PD-1) by monoclonal antibodies (mAbs) can enhance the anti-tumor immune response and result in tumor rejection. Antitumor activity by PD-1 blockade functions in PD-L1+ tumors as well as for tumors that are negative for the expression of PD-L1. This suggests that host mechanisms (ie, expression of PD-L1 in antigen-presenting cells) limit the antitumor response. Consequently, both PD-L1 positive and negative tumors may be targeted using this approach. In humans, constitutive PD-L1 expression is normally limited to macrophage-lineage cells, although expression of PD-L1 can be induced on other hematologic cells as well, including activated T cells. However, aberrant expression of PD-L1 by tumor cells has been reported in a number of human malignancies. PD-L1 expressed by tumor cells has been shown to enhance apoptosis of activated tumor-specific T cells in vitro. Moreover, the expression of PD-L1 may protect the tumor cells from the induction of apoptosis by effector T cells. Retrospective analyses of several human tumor types suggest that tumor overexpression (as measured by IHC) of PD-L1 may permit immune evasion by tumors. PD-L1 expression had been shown to be consistently associated with tumors that are more inflamed and is a major mechanism of immune evasion.

*Reproductive and Developmental Toxicity:* Preliminary new non-clinical safety findings of adverse pregnancy outcomes and infant losses in the absence of overt maternal toxicity have been reported. The findings of increased late stage pregnancy loss and early infant deaths/euthanasia in BMS-936558 (nivolumab) exposed pregnant monkeys suggest a potential risk to human pregnancy if there is continued treatment with BMS-936558 during pregnancy.

**b) Pharmacology:** BMS-936558 (MDX-1106) is a fully human, IgG4 (kappa) isotype, mAb that binds PD-1. Blockade of the PD-1 pathway by BMS-936558 was studied using the mixed lymphocyte reaction (MLR). PD-1 blockade resulted in a reproducible enhancement of both proliferation and interferon release in the MLR. The effect of BMS-936558 on antigen-specific recall response was investigated using a CMV-restimulation assay with human PBMC, and was evaluated by ELISA. These data indicated that BMS-936558, versus an isotype-matched control antibody, augmented interferon secretion from CMV-specific memory T cells in a dose-dependent manner. PD-1 blockade by BMS-936558 has therefore been pursued as a promising avenue for immunotherapy of tumors.

**c) Clinical results:** Two studies contributed to most of the clinical experience with BMS-936558 in subjects with malignancies. MDX1106-01 was a Phase 1 single-dose escalation study in subjects (N = 39) with previously treated advanced or metastatic cancer. Subjects received a single dose of BMS-936558 at 0.3, 1, 3, or 10 mg/kg with an option for re-treatment at 3 months. CA209003 (MDX1106-003) is an ongoing Phase 1 multi-dose dose escalation study in subjects with previously treated advanced or metastatic melanoma, RCC, non-small cell lung cancer (NSCLC), colorectal cancer (CRC), or hormone-refractory prostate cancer (HRPC). 169 subjects have received at least one dose

of BMS-936558 intravenously every 2 weeks at doses of 0.1, 0.3, 1, 3, or 10 mg/kg. During the dose escalation portion of the study, subjects were treated at three dose levels: 1, 3, and 10 mg/kg. Initial cohort expansions occurred in each tumor type at the highest tolerable dose evaluated (10 mg/kg) as well as in melanoma at 1 mg/kg and 3 mg/kg. The protocol was subsequently amended (Amendment 4), to include expansion cohorts in RCC at 1 mg/kg, melanoma at 0.1, 0.3, and 1 mg/kg, and NSCLC (squamous and non-squamous) at 1, 3, and 10 mg/kg.

**d) Safety Summary:** No MTD was identified in CA209003. The maximum dose level evaluated was 10 mg/kg. The most frequent AEs were fatigue (49%), diarrhea (29%), decreased appetite (27%), nausea (26%), vomiting (22%), and rash (21%). There was no pattern in the incidence, severity or relationship of adverse events to the BMS-936558 dose level. Any grade drug-related AEs were experienced by 57% of subjects. The most common drug related AEs were fatigue (22%), rash (15%), pruritus (11%), and diarrhea (9%). Most drug-related AEs were Grade 1 or Grade 2 in severity. Similar to the overall AE profile, there was no apparent relationship in the incidence or severity of drug-related AEs to BMS-936558 dose level. There were no apparent differences in the frequency of adverse events based on subjects' tumor type. As of the clinical cut-off date (31-May-2011), 18 deaths have been reported. Death was considered secondary to disease progression and unrelated to BMS-936558 in 16 subjects. One death was considered secondary to sepsis (Grade 5)/pneumonitis (Grade 4). The fatal sepsis was considered unrelated to study drug; however the preceding pneumonitis was considered related to BMS-936558. One death was considered secondary to ischemic cardiomyopathy and considered unrelated to BMS-936558. Subsequent to the clinical cut-off date, other cases of pneumonitis, including 2 fatal cases, have been reported. Additional details regarding these cases are provided in the Investigator Brochure, Section 5.

## 1.5 Summary of Rationale for proposed study

*A validated molecular target for therapy yet failure to translate:* The epigenetic protein DNA methyltransferase 1 (DNMT1) has been extensively validated in pre-clinical studies as a molecular target for treatment of NSCLC, since inhibition of DNMT1 produces cell cycle exits that do not require p16/p53, but instead utilize physiologic, cell maturation-related MYC antagonists (e.g., p27/CDKN1B, reviewed in). The extensively reproduced pre-clinical data prompted multiple clinical trials of the DNMT1-depleting drugs decitabine and 5-azacytidine to treat solid tumor malignancies, however, results have been disappointing (response rates typically <10%), so Dec is not approved to treat any solid tumor malignancy, despite several clinical trials over decades. We hypothesize that this failure to translate from the lab into clinical benefit is not because of improperly executed pre-clinical science, but because of a failure to rigorously capitalize on basic pharmacologic properties of Dec.

*Bridging to delayed effect of immune therapy with non-cytotoxic tumor cytoreducing therapy:* Delayed effects have been reported with immune therapies like nivolumab. Non-cytotoxic, p53-independent therapy with oral THU-decitabine can potentially bridge this

gap while sparing the immune-system, thereby contrasting with traditional cytotoxic therapy.

*Immune priming effect of DNMT1 inhibition:* The clinical trials with Dec and 5-azacytidine showed dismal responses. However patients on these trials had durable responses to their subsequent line of therapy, particularly immune-checkpoint inhibitors. Several of these patients had an unusually prolonged duration of responses. This raised the possibility of the epigenetic treatment “priming” the tumors for subsequent therapies. In trials evaluating DAC, an increase in the expression of tumor specific cancer testis antigens (NY-ESO-1 and MAGE-A3) were noted in the sequential biopsies Thus an “immune priming” effect of epigenetic therapy has been proposed. In in-vivo mice tumor models treatment with low dose Dec increased IFN- $\gamma$  producing T lymphocytes in the tumors and resulting in an anti-tumor response. In addition, pre-clinical studies show that 5-azacytidine can promote tumor infiltrating myeloid cells and promote differentiation into mature immune-stimulatory antigen presenting cells (APC) in addition to constitutively overexpressing HLA class I antigens and other co-stimulatory molecules. Increased APCs can orchestrate an immune cascade by activating cytotoxic T-Cells resulting in an anti-tumor effect. Furthermore the negative immune checkpoints, including PD1 on T-cells appear to be tightly regulated by methylation thus influencing cytotoxic T-cell differentiation. Recently, increased activation of immune evasive pathways mainly PD-1/PDL1 and CTLA4 was demonstrated in leukemia cells with treatment of Dec. There is an ongoing phase II clinical trial evaluating Azacitidine and entinostat combination with nivolumab, an anti-programmed death-1, antibody (NCT01928576). In addition, there was a recently concluded phase II trial with the combination of 5azacytidine and entinostat vs. observation in resected stage I NSCLC (NCT01207726) the results of which are awaited. With the pharmacology of oral THU-Dec that is optimized for non-cytotoxic DNMT1-depletion, we suspect that such immune-priming will be even more meaningful and significant.

There are no other drugs available for clinical use that have been designed and optimized for non-cytotoxic epigenetic-differentiation therapeutic effects. Thus, this proposal constitutes a first pharmacologically rational attempt to translate extensive scientific data regarding the value of DNMT1 as a molecular target for therapy that can potentially be effective even in advanced NSCLC that is refractory to current therapies, including the latest alternative molecular targeted therapies. Moreover, by augmenting expression of neoantigens via epigenetic mechanisms, this non-cytotoxic therapy is a rational platform for increasing the response rate and effectiveness of immune-checkpoint inhibitors in NSCLC.

Thus, our overall objective is to evaluate if oral THU-low dose Dec based on rational pharmacology can realize the potential for DNMT1 as a molecular target in NSCLC, with a distinctive p53/p16-independent pathway of action achieving efficacy in refractory disease with excellent safety profile and augment the efficacy of nivolumab by immune priming.

## **1.6 Background and rationale of correlative studies**

### **a) Correlatives in biopsy tissue**

All the tissue based immunological correlatives PD-L1 expression and other exploratory correlatives will be performed in the Translational Immuno-oncology Laboratory lab at the Yale University. This laboratory is specialized in measurement of immune biomarkers and has access to CLIA-compliant facilities.

*i) Measurement of Tumor infiltrating immune cells on pre-treatment and post treatment biopsies:* The automated quantitative spectral multiplexing platform for evaluation of immune biomarkers is highly novel. We have previously developed and validated ways to reproducibly measure and quantify TILs and immune biomarkers by QIF. To understand the tumor immune landscape, we will characterize the immune infiltrates in the samples using a previously described and validated assay to objectively interrogate different lymphocyte subsets. This assay comprises the simultaneous staining and measurement of tumor cells (cytokeratin), T cells (CD3), cytotoxic T cells (CD8) and B lymphocytes (CD20). The signal intensity and amount of cells will be measured using informatic tools as described for PD-L1. These will be done in collaboration with Tumor immunology lab at Yale to develop and validate several immune biomarker panels for potential use in the clinical setting. This collaboration will expand on our previous work.

*ii) Measurement of several immune biomarkers in the tumor and stromal compartments on pre-treatment and post treatment biopsies:* PD-L1 expression will be determined for all patients on pre-treatment samples per standard of care using the DAKO PD-L1 assay in the Yale CLIA lab. Positivity will be determined by the presence of any (non-nuclear) PD-L1 signal present in intact tumor and/or stromal cells within the tumor region of the tissue examined, as evaluated by a pathologist in preparations stained with chromogenic immunohistochemistry for PD-L1 and counterstained with hematoxylin. Operationally, a positivity threshold of signal present in >1% of cells will be used. An additional 3-tiered semi-quantitative categorical result will be rendered by the pathologist based in the estimation of the percentage of positive cells including 1+ (<30%), 2+ (30-<60%) and 3+ (60-100%). PD-L1 negative cases will be those with absence of any detectable signal in the sample tested and with appropriate tissue and staining controls.

In addition, to chromogenic PD-L1 IHC using novel platform we can increase specific staining of multiple tissue biomarkers (PD-L2, B7H4, TIM-3, VISTA, LAG-3, IDO-1 etc) and able to reach 6-plex and beyond in a single image retaining the morphologic context of the tumor. The incorporation of such novel approaches could positively impact the value of tissue biomarkers determination for anti-cancer immunotherapies. Finally, additional correlative studies using novel approaches with higher sensitivity and throughput such as the Luminex assay and CyTOF massspect based cytometry will be pursued once these platforms are appropriately standardized.

*iii) mRNA expression profiling:* We will evaluate changes in mRNA expression profiles in FFPE tumor samples obtained before and after treatment with THU-Dec using the Nanostring and Counter Pancancer panel. Specifically, we will assess variations in immune-related transcripts and changes in MYC, as well as upregulation of the terminal differentiation markers and tumor specific antigen changes (Cancer testis antigens). We will also look at changes in DNMT1, DCK, UCK2 and CDA expression to study the intended pharmacodynamics of the THU-Dec combination

*iv) Next Generation Sequencing for T-cell receptor clonality:* TCR sequencing and clonality quantification on pre-and post-treatment samples will be performed using ImmunoSeq assay in a multiplexed PCR method using forward primers specific to TCR V $\beta$  gene segments and reverse primers specific to TCR J $\beta$  gene segments. In addition, using Immune Repertoire Capture™ (IRC™) technology we will evaluate immune response enabling the identification and generation of functional human antibodies and TCRs. This delivers an unparalleled quantitation of the adaptive immune response. This will be done in collaboration with Atreca Inc.

*v) Pharmacodynamic analyses:* The intended molecular pharmacodynamic effect of oral THU-decitabine is depletion of DNMT1 in tumor tissue. This will be measured by QIF. DNMT1-depletion is expected to induce p53-independent cell cycle exits, with downregulation of MYC and upregulation of p27/CDKN1B. This will be measured by QIF also. Finally, the intracellular accumulation of decitabine to deplete DNMT1 depends on relative expression in the cancer cells of pyrimidine metabolism enzymes DCK, CDA and UCK2, and also the growth fraction of the malignancy, measured by surrogates such as KI67. These parameters will also be measured by QIF.

**b) Correlatives in blood:**

*i) Phenotypic character of PBMC:* To be performed by GenOptix. Multiplex T cell phenotyping flow cytometry panels: We will design a broad T-cell flow cytometry panel composed of multiple exhaustion markers, checkpoint receptors and activation markers. Non-biased automated algorithms will be used to determine T –cell signatures predictive of response and resistance to immunotherapies. The putative markers in the panel may include CD3, CD4, CD8, CD45RO, CD45RA, CCR7, CD95, CD27, CD25, CD57, CD107, CD69 CD11A, TIM3, HLA-DR, PD-1, LAG3, OX40, ICOS, CCR4, CXCR3, CCR6, BIM, EOMES, CTLA-4. In addition to T-cells, we will evaluate other immune cell subsets including DCs, monocyte populations, and NK cells. A whole blood immunophenotyping assay will quantify the absolute number and proportion of NK cells (CD56+CD3-), NKT cells (CD56+CD3+), B cells (CD19+), and monocytes (CD16+). In addition, both myeloid (CD45+HLADR+ CD11c+CD123-) and plasmacytoid (CD45+HLA-DR+CD11c-CD123+) dendritic cell (DC) frequencies will be measured in this precision-validated multiparameter flow cytometric assay. In addition, PBMCs will be cryopreserved for future potential studies using platforms such as Mass cytometry (CyTOF), IRC™ and CIBERSORT, and will be correlated to the immunologic response, clinical response, and survival data.

*ii) Serum proteomic and ctDNA correlatives:* Exploratory proteomic analysis using MALDI ToF mass-spectrometry and ProTS will be performed in collaboration with Biodesix and the [name] lab at Johns Hopkins on baseline and on treatment plasma samples at time points defined in the protocol from patients in the study.

PBMCs, Serum and plasma will be banked for other potential correlatives

## **2.0 OBJECTIVES & HYPOTHESES**

**Hypothesis:** We hypothesize that the combination of nivolumab with non-cytotoxic low dose oral Dec with THU achieves immune priming and improves clinical efficacy of nivolumab.

**Primary objective:** To determine if non-cytotoxic oral THU-Dec when combined with nivolumab can improve objective response rates of nivolumab

**Secondary objectives:**

- i) To evaluate clinical efficacy end points and toxicity of oral THU-Dec in combination with nivolumab;
- ii) To evaluate the Immune priming effect of THU-Dec combination therapy by functional and phenotypic circulating immune cell characterization and changes in the immune contexture in the tumor tissue
- iii) To evaluate hypotheses regarding mechanisms of resistance and predictive biomarkers for response to nivolumab

### 3.0 STUDY DESIGN

**3.1 Study design:** This is a Phase 2 randomized two arm trial of nivolumab alone or in combination with THU-Dec, in previously treated patients with stage IV Non-Small Cell Lung Cancer (NSCLC). The primary goal of this trial is to compare the efficacy of oral THU-Dec as a way of enhancing the anti-tumor immune response to nivolumab to that of nivolumab alone. The primary efficacy endpoint is overall RECIST v1.1-defined response. To accomplish this goal 60 patients will be randomized 2:1 to THU-Dec plus nivolumab or nivolumab only respectively.

**3.2 Statistics and Sample size justification:** The primary goal of this trial is to compare the efficacy of immune priming with oral tetrahydrouridine (THU) plus decitabine (THU-Dec) and immune check-point inhibitor nivolumab (THU-Dec+nivolumab) to that of nivolumab alone. The primary efficacy endpoint is overall response. To accomplish this goal 60 patients will be randomized 2:1 to THU-Dec+nivolumab versus nivolumab alone (standard of care) respectively. The purpose of the nivolumab alone arm is to support the notion that the population studied is typical of the general population for which nivolumab has an established response rate of 20%. If the THU-Dec+nivolumab arm has a response rate of 35% or higher, we will consider it worthy of further investigation in a phase III trial. Thus, using a two-stage design (<http://www.swogstat.org/stat/public/twostage.htm>), with  $\alpha = 0.1$  and  $\beta = 0.2$ , we compute that 20 patients will be needed in each of two stages in the THU-Dec+nivolumab arm. If, after the 1st stage of 20 patients in the THU-Dec+nivolumab arm, 2 or fewer respond, the trial will be stopped and the null hypothesis that THU-Dec+nivolumab is no better than nivolumab will be accepted, else the trial continues for an additional 20 patients, at the end of which if 13 or more respond of the 40

patients in the THU-Dec+nivolumab arm, the null hypothesis is rejected and experimental arm of THU-Dec+nivolumab is recommended for further study.

As an additional exploratory analysis we will compare response rates between treatment groups. We expect a 20% response rate in our control arm of 20 patients. The 95% confidence interval of the proportion  $4/20$  is 7% to 44%. It thus includes our treatment arm expected response rate of 35%. It is therefore very unlikely that our control arm will disprove our assumption that our sample population has a historical response rate of 20%. Thus, to increase the likelihood of gaining some information from our control arm, differences in proportions will be compared between arms. Using a calculator for [two arm binomial studies](#) we compute that the power to detect a difference in rates between our control arm and our treatment arm of 40 patients, assuming one-sided tests,  $\alpha=0.10$  and holding the treatment arm response rate at 35%, is, respectively, 89%, 70%, 50%, 32% and 18% for control response rates of 5%, 10%, 15%, 20%, and 25%. Thus, if our control arm rates are  $<15\%$ , we have  $>50\%$  chance of detecting a difference in response. In addition, we will evaluate the PD-L1 expression in both the control and treatment arm after every 20 patients. If there is  $>10\%$  difference in the PD-L1 status between the groups, we will stratify randomization by PD-L1 status for additional patients to balance the PD-L1 status.

Secondary endpoints include progression-free survival (progression is defined as progression by both RECIST v1.1), overall survival, and toxicity. Progression-free and overall survival will be summarized using the Kaplan-Meier method. Adverse events will be graded using CTCAE version 4.0 criteria, categorized by organ system, and summarized using frequency counts and percentages. With 20 patients treated with nivolumab only and 40 with THU-Dec+nivolumab the probability of observing at least one toxicity of a particular type and/or grade on each arm is 64% and 87%, respectively, if the risk of such an event is 5%, i.e.  $0.64 = (1-0.95^{20})$ .

Methods such as Fisher's exact test, chi-square tests, logistic regression (categorical data), the log-rank test and proportional hazards models (time to event data) will be used to compare patient groups. These analyses are primarily exploratory and it is acknowledged that they will have relatively low statistical power.

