### **6.5 Stopping Rule**

If 3 of the first 5 patients in the THU-Dec + nivolumab arm are removed from study for grade 3/4 non-hematologic toxicity or toxicities prior to cycle 2 that are likely attributable to THU-Dec, the study will be terminated.

The study incorporates a two-stage design in the experimental THU-Dec + nivolumab arm. If after the 1st stage of 20 patients in the THU-Dec+nivolumab arm, 2 or fewer respond, the trial will be stopped and the null hypothesis that THU-Dec+nivolumab is no better than nivolumab will be accepted, else the trial continues for an additional 20 patients.

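### Sections 3.2 and 6.5 word the two-stage null as a comparison with nivolumab, but the rule tests only whether the THU-Dec arm's response rate exceeds 20%

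*Combined protocol and SAP*

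**What the plan says.** The primary objective in Section 2.0 is comparative: "To determine if non-cytotoxic oral THU-Dec when combined with nivolumab can improve objective response rates of nivolumab". Sections 3.1 and 3.2 likewise give the primary goal as a comparison with nivolumab alone.

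Section 3.2 then sets a two-stage rule, 20 + 20 patients, in the THU-Dec+nivolumab arm, with alpha 0.1, beta 0.2 and a 35% target. With 2 or fewer responders of 20, "the null hypothesis that THU-Dec+nivolumab is no better than nivolumab will be accepted". With 13 or more of 40, "the null hypothesis is rejected and experimental arm of THU-Dec+nivolumab is recommended for further study". Section 6.5 restates stage 1: "the null hypothesis that THU-Dec+nivolumab is no better than nivolumab will be accepted, else the trial continues for an additional 20 patients".

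The benchmark is disclosed: "nivolumab has an established response rate of 20" per cent. So is the role of the 20 controls: "The purpose of the nivolumab alone arm is to support the notion that the population studied is typical of the general population". Section 3.2 adds: "It is therefore very unlikely that our control arm will disprove our assumption that our sample population has a historical response rate of 20" per cent. It therefore plans an exploratory comparison, "to increase the likelihood of gaining some information from our control arm, differences in proportions will be compared between arms", at one-sided 0.10, with printed powers of 89, 70, 50, 32 and 18% for control rates of 5 to 25% against 35%. Fisher's exact test, chi-square tests and logistic regression are listed for categorical data; none is assigned to ORR.

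**The concern.** A null that says one regimen is no better than another concerns a difference between two rates. The rule looks at one rate. The two coincide only if nivolumab alone gives exactly 20% in the patients enrolled, and the plan itself says the control arm is unlikely to show otherwise.

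In a randomized trial with a comparative objective, readers will take acceptance or rejection of that null as a between-arm result. If the true control rate is somewhat above 20%, an inert THU-Dec can reject the written null more often than the stated alpha. If it is below 20%, an arm that improves on nivolumab but reaches only 20% can be labelled no better than nivolumab. Not advancing such an arm is what the bar intends; the label is what would be wrong.

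**Working it through.** **Inputs (Section 3.2).** Benchmark 20%, target 35%, alpha 0.10, beta 0.20; stop at ≤2/20, reject at ≥13/40, THU-Dec arm only; 40 v 20 patients. Nivolumab rates of 23% and 25% are assumptions; 25% is the top of the control range in the plan's power statement.

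**1. The plan's rule.** With true ORR p in the THU-Dec arm,

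P(go) = Σ (x = 3 to 20) C(20,x) pˣ(1−p)²⁰⁻ˣ × P(Bin(20,p) ≥ 13−x).

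At p = 0.20 this is 0.043, within alpha 0.10. At p = 0.35 it is 0.685, short of the 0.80 implied by beta 0.2; that shortfall is a separate matter and this point does not rely on it. The control rate appears nowhere in the formula, so the hypothesis being tested is p ≤ 0.20.

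**2. Inert THU-Dec.** Let both arms share the true rate p. The last column also requires the lower limit of the 80% two-sided Newcombe interval for the ORR difference to exceed 0, by joint enumeration with Bin(20,p) controls.

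| True ORR, both arms | P(reject the written null) | P(reject and Newcombe lower limit > 0) |
|---|---|---|
| 20% | 0.043 | 0.020 |
| 23% (assumed) | 0.110 | 0.039 |
| 25% (assumed) | 0.179 | 0.053 |

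P(go) passes 0.10 at p = 22.7%.

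**3. Can the controls reveal the shift?** P(Bin(20,0.20) ≥ 8) = 0.032 and P(≥ 9) = 0.010, so contradicting 20% at exact one-sided 0.025 takes 9/20. At a true 25%, P(≥ 9) = 0.041. This agrees with the plan's concession. At 25% in both arms, the probability of rejecting with an observed control ORR at least as high as the THU-Dec ORR is 0.0314, which is 0.0314/0.1788 = 17.6% of rejections. For example, 13/40 v 7/20 (32.5% v 35%) still rejects.

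**4. At the go boundary, 13/40 v 4/20.** The difference is 0.325 − 0.200 = 0.125. The 80% Wilson limits are 0.239 to 0.425 and 0.110 to 0.335.

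- Lower: 0.125 − √[(0.325−0.239)² + (0.335−0.200)²] = −0.036
- Upper: 0.125 + √[(0.425−0.325)² + (0.200−0.110)²] = 0.260

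The rule rejects while the randomized estimate is +12.5 points (−3.6 to 26.0). For 13/40 v 5/20 it is +7.5 points (−8.9 to 21.8).

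**5. Exploratory comparison (secondary).** The printed powers are reproduced by a normal approximation with the control n cut to 20 − 3/(2d), where d is the difference in rates. At control 20%, d = 0.15, n = 10 and the pooled rate is 0.30:

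Φ[(0.15√10 − 1.2816√(1.5 × 0.30 × 0.70)) / √(0.20 × 0.80 + 0.35 × 0.65/2)] = Φ(−0.468) = 0.320.

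All five come to 0.885, 0.704, 0.500, 0.320 and 0.178. That this is the calculator's method is an inference. Exact powers from the full 21 × 41 table at one-sided 0.10:

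| Control ORR (v 35%) | Printed | Fisher | Uncorrected chi-square |
|---|---|---|---|
| 5% | 89% | 91% | 96% |
| 10% | 70% | 74% | 83% |
| 15% | 50% | 53% | 66% |
| 20% | 32% | 35% | 47–48% (0.475) |
| 25% | 18% | 21% | 31% |

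The size of the chi-square test at common rates of 10 to 35% is 0.097 to 0.105. At 15/40 v 4/20 the one-sided p-value is 0.140 by Fisher and 0.085 by chi-square, so the choice of test can decide the result.

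**The case against.** The 20% benchmark, the 35% target and the limited role of the controls are all set out before the null is worded, so no better than nivolumab can be read as shorthand for no better than 20%. At the plan's own 20% the error is 0.043. On rejection the plan says only that the arm is recommended for further study; it prescribes no superiority claim. Drift in a historical rate affects any single-arm benchmark, and rewording leaves P(go) at 25% unchanged at 0.179. The between-arm analysis is declared exploratory and of low power, and its printed powers understate the trial rather than oversell it.

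Most of this stands, and it sets the weight. It does not remove the fault: two sections still prescribe accepting or rejecting a comparative hypothesis on data from one arm, under a comparative objective.

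Three stronger readings are tempting and are not supported:

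- *The design is hidden.* Section 3.2 states the benchmark and the control arm's purpose openly.
- *The go/no-go bar is invalid or its alpha is inflated.* The probabilities above 0.10 need nivolumab rates that the plan does not assume.
- *Stage 1 would reject a demonstrated benefit.* An arm with true ORR 20% stops at stage 1 with probability 0.206, but the label is wrong only if the control rate is below 20%. With 10 controls by then (assumed from 2:1), 2/20 v 0/10 is +10 points with 80% interval −5.2 to 21.8, which would not show a benefit either. What remains is that accepted claims more than 2/20 in one arm can show.

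**Conclusion.** The point holds as a minor error of statement. The null in Sections 3.2 and 6.5 is comparative, the rule tests ORR ≤ 20% in one arm, and the prescribed conclusion does not follow from the rule. The plan never writes ORR ≤ 20% as the null; it follows from the stated benchmark and from the form of the rule.

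The size depends on the unknown nivolumab rate in the enrolled patients: the written null is falsely rejected with probability 0.043 at 20%, and 0.110 or 0.179 if that rate were 23% or 25%. Those two rates are assumptions, and the documents do not say that they are likely. The cut-offs and the recommendation rule are not in question here.

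The unassigned test for the exploratory comparison is a lesser matter. The printed powers are a conservative approximation and are not the exact power of Fisher's test or of the uncorrected chi-square test.

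**What to change.** **Main change.**

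- In Sections 3.2 and 6.5, state the null as: the ORR in the THU-Dec+nivolumab arm is at most 20%. Replace accepted with not rejected. Leave both cut-offs and the sample size as they are.
- In Sections 3.1 and 3.2, say that the comparative goal is addressed by the randomized ORR difference (40 v 20) with an 80% two-sided Newcombe interval, which matches one-sided 0.10, and that no statement of superiority over nivolumab will be made from the two-stage rule alone. The same goal wording appears in the Protocol Summary and should be aligned.

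**Cost.** Text and a line of code; no patients. The claim becomes narrower: at 35% v 20%, go has probability 0.685, but go with the lower limit above 0 has 0.419 (0.290 if control is 25%). The interval is approximate, with one-sided error of 0.097 to 0.107 at common rates of 10 to 35%.

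**Secondary change.** In Section 3.2, name one test for the exploratory ORR comparison before data are seen, and print its exact power in place of 89/70/50/32/18%. The uncorrected chi-square test is already on the plan's list; its exact powers are 0.958, 0.833, 0.658, 0.475 and 0.314. The cost is giving up a later choice of test and accepting a size that can slightly exceed 0.10.
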